8.2.2 Hierarchical Testing Strategy for Secondary Efficacy Endpoints

If the test of the treatment effect on the primary efficacy endpoint is statistically significant, the analysis of the key secondary efficacy endpoints will proceed using the following step-down closed testing procedure to maintain the family-wise Type I error rate at significance level $\alpha = 0.05$ (2-sided):

- Step 1: Test the treatment effect at a significance level of 0.05 on duration of severe thrombocytopenia defined as a platelet count $<50 \times 10^9/L$ during the period after post-chemotherapy IP treatment in Cycle X+1 through Chemotherapy Day of Cycle X + 2; if successful, proceed to Step 2; otherwise stop at Step 1.
- Step 2: Test the treatment effect at a significance level of 0.05 on change in platelet count from baseline (qualifying chemotherapy cycle [Cycle X]) (nadir) to Cycle X + 1 (nadir); if successful, proceed to Step 3; otherwise stop at Step 2.
- Step 3: Test the treatment effect at a significance level of 0.05 on proportion of subjects who do not have major or non-major clinically relevant bleeding during the period after post-chemotherapy IP treatment in Cycle X+1 through Chemotherapy Day of Cycle X + 2; if successful, proceed to Step 4; otherwise stop at Step 3.
- Step 4: Test the treatment effect at a significance level of 0.05 on proportion of subjects who do not receive platelet transfusion during the period after post-chemotherapy IP treatment in Cycle X+1 through Chemotherapy Day of Cycle X + 2.

8.3 Other Efficacy Analysis

The other efficacy endpoints include the following during the period after post-chemotherapy IP treatment in Cycle X+1 through Chemotherapy Day of Cycle X+2:

- Proportion of subjects who do not have a chemotherapy dose reduction that is $\geq 15\%$ due to thrombocytopenia;
- Proportion of subjects who do not have a chemotherapy delay that is ≥ 4 days due to thrombocytopenia;
- Proportion of subjects with a pre-defined post-baseline nadir platelet count (i.e., subjects with the lowest platelet count <10 , <25 , <50 , <75 , <100 , and $\geq 100 \times 10^9/L$ at any time);
- Proportion of subjects achieving a pre-defined post-baseline maximum platelet count (i.e., subjects with the highest platelet count ≤ 400 , >400 , and $>600 \times 10^9/L$ at any time).

Confidential

Categorical variables (eg, proportion) will be summarized and analyzed in the similar manner as the primary efficacy endpoint. If the data is sparse where the approximative methods cannot be applied, the Fisher's Exact test will be used instead.

8.4 Sensitivity Analysis of Primary Efficacy Endpoint

The following sensitivity analyses will be performed for the primary efficacy endpoint:

- The difference in the proportion of responders between the avatrombopag and placebo groups will be tested using the Fisher's Exact test;
- The primary efficacy analysis will be repeated using the observed case, i.e. missing data will be excluded from the analysis.

8.5 OLE Period Efficacy Analysis

For the OLE period (start of pre-chemotherapy IP dosing of Cycle X+3 and onward), the following efficacy endpoints will be summarized descriptively for subjects randomized to avatrombopag and subjects randomized to placebo separately and overall:

- Proportion of subjects who meet the primary efficacy criteria (i.e., no platelet transfusion, no chemotherapy delay by ≥ 4 days due to thrombocytopenia, no chemotherapy dose reduction by $\geq 15\%$ due to thrombocytopenia) overall and in each cycle
- Proportion of subjects who do not receive a platelet transfusion overall and in each cycle
- Proportion of subjects who do not have a chemotherapy dose reduction ($\geq 15\%$) due to thrombocytopenia overall and in each cycle
- Proportion of subjects who do not have a chemotherapy delay (≥ 4 days) due to thrombocytopenia overall and in each cycle
- Proportion of subjects who do not have major or non-major clinically relevant bleeding overall and in each cycle
- Duration of severe thrombocytopenia (i.e., platelet count $< 50 \times 10^9/L$) overall and in each cycle
- Actual and change from baseline values of platelet count in each cycle (nadir)

These analyses and summaries will be provided in a similar manner to the Double-Blind/Observational period.

Similar analyses and summaries will be provided for the entire study (Double Blind/Observational Period + OLE) for subjects randomized to avatrombopag 60 mg group only.

8.6 Subgroup Analyses

The primary efficacy analysis will be repeated for the following subgroups:

- Age (< 65 years, $65- < 75$ years, $75- < 85$ years, $85+$ years)
- Sex
- Race (White vs Non-White)
- Number of eligible chemotherapy agents (1 vs ≥ 2)
- Tumor type (ovarian cancer, lung cancer, bladder cancer)
- Previous chemotherapy regimens (0 vs 1 vs 2)
- Region (United States, Europe, China)

Confidential

8.7 Interim Analysis

No formal interim efficacy analysis is planned for this study. An independent Data Safety and Monitoring Board (DSMB) has been convened for this study to monitor safety on a periodic basis. A separate DSMB charter describes the scope of the DSMB's data review as well as rules governing the DSMB.

9. Safety Evaluation

Safety and tolerability will be assessed by examining exposure/treatment compliance, the incidence of adverse events, clinical laboratory parameters, vital signs, and other pertinent safety data using the SAF.

9.1 Exposure and Treatment Compliance

Exposure and treatment compliance will be separately summarized for the Double-Blind period, the OLE period, and the entire study.

The number of doses (both descriptively and categorically) will be summarized for each study period.

Treatment compliance during the relevant study period per subject will be calculated as $(\text{number of tablets taken}/\text{number of tablets expected}) \times 100$. The treatment compliance will be summarized descriptively and also presented categorically (e.g. number and percentage of subjects with <80%, 80-100%, and >100%). Number of tablets taken will be determined as the number of tablets dispensed minus the number of tablets returned that are recorded in the eCRF.

Duration of exposure (in days) will also be summarized descriptively per study period and computed as the last dose day – the first dose day +1. For the OLE period and entire study, duration will also be summarized by categories (≤ 10 days, 11-20 days, 21-30 days, 31-40 days, etc.)

The number and percentage of subjects receiving Cycle X+1 chemotherapy, Cycle X+2 chemotherapy, etc. will be summarized in the relevant study period tables.

A data listing will provide details of subject exposure for the Double-Blind, the OLE periods, and the entire study. Listings of study drug administration for the Double-Blind period and study drug accountability for the OLE period will also be provided.

9.2 Adverse Events

Adverse events (AEs) will be coded using MedDRA version 23.0. The coding may be updated according to newly released versions of the dictionary.

Severity of AEs is categorized according to the National Cancer Institute Common Terminology Criteria for Adverse Events (NCI-CTCAE) version 5.0.

For investigator determined relationship to study drug, AEs are classified as "Related" or "Not Related".

AEs leading to discontinuation of avatrombopag/placebo are AEs where action taken is designated as "Drug Withdrawn" in the eCRF.

Two categories for Adverse Events of Special Interest (AESI) will be summarized and are defined as:

1. Thromboembolic events - All adverse events with MedDRA PT belonging to SMQ 'Embolic and thrombotic events'

Confidential

2. Bleeding Events - MedDRA PT belonging to 2nd level SMQ 'Haemorrhage terms (excl laboratory terms)'

Tabular summaries of adverse events will be provided for the Double-Blind/Observational period, OLE period, and the entire study separately and will only include treatment-emergent adverse events (TEAE). TEAEs are defined as AEs occurring after the first dose of study treatment.

Listings will include all adverse events reported after the consent form is signed (both TEAE and non-TEAE). A flag will be included in the listings to designate whether an adverse event is treatment-emergent.

Overview summary tables by treatment group will include the number and percentage of subjects with at least one:

- TEAE
- TEAE related to study drug
- Serious TEAE
- Grade 3+ TEAEs
- TEAE leading to study drug discontinuation
- TEAE of special interest
- Deaths

Summary tables of TEAEs by System Organ Class (SOC) and Preferred Term (PT) will be provided for:

- TEAE (by SOC and PT and by descending frequency of PT)
- TEAEs related to study drug
- Grade 3+ TEAEs
- Serious TEAE
- TEAE of special interest
- TEAE leading to study drug discontinuation

Listings of all adverse events by treatment group will be provided and will include information such as the patient identifier, SOC, PT, reported term, date of onset/stop, duration of the event, TEAE, seriousness, severity, action taken, outcome, causality and relationship.

Listings of adverse events will be provided for the following categories:

- All Adverse Events
- AEs related to study drug
- Grade 3+ AEs
- Serious AEs
- AEs of special interest
- AEs leading to study drug discontinuation

A listing of deaths will be provided which will include any death details available in the eCRF.

Confidential

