### 3.2 Study Duration and End of Study

The study will consist of the following periods:

- Double-Blind Treatment Period and Observational Period of approximately 8 to 9 weeks,
- Optional OLE Period until the subject's current chemotherapy regimen changes or the subject completes chemotherapy, and
- Long-Term Follow-Up Period of up to 5 years.

The end of study ("study completion") is defined as the date of the last protocol-specified visit/assessment (including telephone contact) for the last subject in the Long-Term Follow-Up Period.

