3.2.2 Observational Period

Cycle X + 2 will be an Observational Period. The Observational Period is designed to enable assessment of whether the subjects meet the chemotherapy dose modifications or dose delay components of the composite primary endpoint while reducing decision-making bias for chemotherapy dose modifications or delays. Subjects in the Observational Period will not receive any IP pre- or post-Chemotherapy Day in Cycle X + 2.

For subjects not continuing into the optional OLE Period, a Follow-Up Visit will occur prior to (within 3 days) Chemotherapy Day in Cycle X + 3. For these subjects, their participation in the Observational Period will conclude after they complete the Follow-Up Visit and at that point they will enter the Long-Term Follow-Up Period (LTFU).

If Cycle X + 2 is the subject's last chemotherapy cycle, a Follow-Up Visit will occur at 30 days (± 3 days) after Chemotherapy Day in Cycle X + 2.

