3.2.3 Optional Open-Label Extension Period

Subjects who complete the Double-Blind Treatment Period and the Observational Period will be eligible to enter an optional OLE Period at 5 days prior to Cycle X + 3, if they fulfill the inclusion criteria and do not meet any exclusion criteria for the optional OLE Period. Subjects must continue to fulfill the inclusion criteria and to not meet any exclusion criteria prior to pre-chemotherapy IP treatment in each enrolled open-label cycle to continue in the OLE Period.

All subjects will receive avatrombopag once daily for 5 days prior to Chemotherapy Day in Cycle X + 3. Subjects will also receive avatrombopag once daily for 5 days immediately following Chemotherapy Day. Avatrombopag will not be administered concurrently with chemotherapy on Chemotherapy Day.

During the study, if the subject has a platelet count $>400 \times 10^9/L$, IP dosing will be stopped temporarily. Dosing may be restarted following discussion with the Medical Monitor.

[figure not shown]
Subjects may repeat this treatment sequence and continue in the optional OLE Period until the end of their current chemotherapy regimen.

Confidential

Subjects will have a Follow-Up Visit at 30 days (± 3 days) after the last dose of IP treatment of the subject's last chemotherapy cycle.

Figure 3. Treatment Schedule for Optional Open-Label Extension Period

Chemo = chemotherapy; IP = investigational product.

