4.4 Treatment Groups

Data displays for the Double-Blind Treatment period/Observational period will have columns for avatrombopag 60 mg dose and placebo groups, unless otherwise specified. Data displays for the optional OLE period will have 3 columns: subjects randomized to avatrombopag 60 mg dose, subjects randomized to placebo, and a total column (all subjects in the optional OLE period receive avatrombopag 60 mg). Data displays for the entire study will include subjects randomized to avatrombopag 60 mg only.

Data listings will generally include Subject ID, Age/Sex/Race, and an indicator of whether the applicable record occurred during the Screening, Double-Blind, Observational, or OLE periods.

5. Study Patients

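### Open-label and entire-study adverse event tables give only crude subject percentages over an unequal number of cycles, and no table covers all avatrombopag exposure

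*SAP*

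**What the plan says.** SAP 9.2 sets out three sets of adverse event tables: "Tabular summaries of adverse events will be provided for the Double-Blind/Observational period, OLE period, and the entire study separately". On the statistic it says: "Overview summary tables by treatment group will include the number and percentage of subjects with at least one", followed by the event types; further tables break these down by SOC and PT. It plans no rate per cycle, no by-cycle table and no time-to-first-event summary. The treatment-emergent window has a start but no stated end: "TEAEs are defined as AEs occurring after the first dose of study treatment".

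The periods differ in length by design.
- **Double-Blind/Observational.** Protocol 3.2 describes a "Double-Blind Treatment Period and Observational Period of approximately 8 to 9 weeks". It covers Cycles X+1 and X+2, and only X+1 is treated: "Subjects in the Observational Period will not receive any IP pre- or post-Chemotherapy Day in Cycle X + 2" (SAP 3.2.2).
- **OLE.** SAP 3.2.3 sets no number of cycles: "Subjects may repeat this treatment sequence and continue in the optional OLE Period until the end of their current chemotherapy regimen". Eligibility is rechecked before each one.
- **Entire study.** SAP 4.4 restricts the columns: "Data displays for the entire study will include subjects randomized to avatrombopag 60 mg only".

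SAP 9.1 tabulates doses, duration of exposure and the number of subjects receiving each chemotherapy cycle, but does not link these to events. Protocol 10.2.2 says that adverse event incidence will be examined over time.

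**The concern.** A percentage of subjects with at least one event mixes the risk per cycle with the number of cycles observed. Setting the OLE or entire-study percentage beside the Double-Blind/Observational one therefore does not show whether the risk per cycle is stable, rising or falling. Repeated treatment is what the OLE is there to describe, and Protocol 9.1.2 names thromboembolic and bleeding events as AESI.

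There is also a gap in coverage. Placebo subjects who enter the OLE receive avatrombopag there, but entire-study displays exclude them. The OLE total column includes them but omits the Cycle X+1 exposure of the avatrombopag arm. No planned table follows every avatrombopag-exposed subject from first dose.

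**Working it through.** The documents give no expected adverse event rate and no expected number of OLE cycles, so there is no figure of the plan's own to reproduce. The risks and cycle counts below are assumptions.

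**1. Crude percentage under constant risk.** Let p be the risk per chemotherapy cycle, constant and independent between cycles. After k cycles the expected percentage is 1 − (1 − p)^k. Double-Blind/Observational has k = 2 (X+1 and X+2). The entire study has 2 plus the number of OLE cycles.

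| Assumed p | Double-Blind/Obs (2 cycles) | OLE, 1 cycle | OLE, 2 cycles | OLE, 4 cycles | Entire study with 4 OLE cycles (6 in all) |
|---|---|---|---|---|---|
| 2% | 4.0% | 2.0% | 4.0% | 7.8% | 11.4% |
| 3% | 5.9% | 3.0% | 5.9% | 11.5% | 16.7% |
| 5% | 9.8% | 5.0% | 9.8% | 18.5% | 26.5% |
| 10% | 19.0% | 10.0% | 19.0% | 34.4% | 46.9% |

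For 80 avatrombopag subjects at p = 5%, all with four OLE cycles, that is about 8 subjects with an event in Double-Blind/Observational (80 × 0.0975 = 7.8) and about 21 in the entire study (80 × 0.265 = 21.2).

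**2. Mixed cycle counts.** At p = 5%, three assumed distributions of OLE cycles, with means of 1.4, 2.0 and 2.7 among entrants, give OLE percentages of 6.9%, 9.6% and 12.9% and entire-study percentages of 12.9%, 14.1% and 17.9%, against 9.8% in Double-Blind/Observational. The OLE figure can thus be lower or higher. The entire-study figure cannot be lower, because it counts the same subjects over a longer period.

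**3. A per-cycle denominator.** Expected cycles at risk up to a first event are the sum of (1 − p)^j for j = 0 to k − 1, which is [1 − (1 − p)^k] / p. First events divided by cycles at risk therefore return p for any k. With p = 5% and k = 6, 100 subjects give 26.5 first events over 26.5 / 0.05 = 530 cycles, or 5.0 per 100. All three mixed distributions also give 5.0, for the OLE and for the entire study.

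**4. The denominator must match the numerator.** Suppose p = 2% per chemotherapy cycle and the Double-Blind/Observational numerator, which includes events in untreated X+2, is divided by treated cycles only. The result is about 4 per 100 (1 − 0.98² = 3.96% over one treated cycle), against 2 per 100 in the OLE. That is a false halving.

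**5. Value of a pooled column.** For an event never seen in n subjects, the one-sided 95% upper limit is 1 − 0.05^(1/n). The sample size section plans 80 avatrombopag and 40 placebo subjects.
- n = 80 (avatrombopag arm alone): 3.7%
- n = 100 (half of placebo enters the OLE): 3.0%
- n = 120 (all of placebo enters): 2.5%

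**The case against.** Much can be said for the plan. No test across periods is planned, and entire-study displays have no placebo column. Adverse event listings carry onset dates, AESI have their own listing, and SAP 9.1 shows how many subjects received each cycle. A few thromboembolic events could be placed by cycle by hand. All of this is true, and it keeps the point modest. But a listing is not a summary, and hand placement does not work for frequent Grade 3+ events. The duration in SAP 9.1 runs from first to last dose, so for the entire study it includes untreated X+2 and is a poor denominator.

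Stronger readings are tempting, and the documents do not support them.
- A reader might infer that the OLE table will make a constant risk look as if it grows on avatrombopag. The comparison table includes X+2, so the OLE percentage is higher only if subjects average more than about two OLE cycles, or if risk arises only in treated cycles. The documents settle neither.
- A reader might infer that the two OLE columns are not comparable. Both groups follow the same continuation rule, and nothing in the documents suggests different cycle counts.
- A reader might extend the fault to the OLE efficacy proportions in SAP 8.5. That section already plans, for example, "Proportion of subjects who do not receive a platelet transfusion overall and in each cycle", and does the same for ISTH bleeding. The overall figures depend on the number of cycles, but the per-cycle figures stand beside them.

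**Conclusion.** The point holds as a gap in the descriptive safety reporting. The OLE and entire-study percentages in SAP 9.2 depend on how many cycles subjects receive and cannot be read as a change in risk. For the same subjects the entire-study percentage can only equal or exceed the Double-Blind/Observational one; the direction for the OLE is open. No table covers all avatrombopag-exposed subjects from first dose.

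The size is illustrative. At an assumed 5% per chemotherapy cycle and four OLE cycles, the same subjects go from 9.8% to 26.5% with no change in risk. This assumes independence between cycles. If events recur in the same subjects the rise is smaller, and with complete dependence there is none. The fall in the zero-event limit from 3.7% to between 3.0% and 2.5% depends on half to all of the placebo subjects entering an optional OLE.

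The randomized Double-Blind/Observational comparison and the primary inference are untouched. This is a cheap improvement, not a flaw in the trial's main conclusion.

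**What to change.** In SAP 9.2, keep the crude percentages and add the following for thromboembolic AESI, bleeding AESI, serious TEAEs and Grade 3+ TEAEs:

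- **(a) By-cycle incidence** for X+1, X+2, X+3 and on, with subjects starting that cycle as the denominator and untreated X+2 shown separately. A single pooled OLE rate cannot show a trend across cycles, so this table is needed as well as (b).
- **(b) Subjects with a first event per 100 subject-cycles at risk**, with an exact Poisson 95% CI. Numerator and denominator must cover the same cycles: X+2 in both or in neither, stated in advance.
- **(c) A column pooling all subjects from their first avatrombopag dose**, which for placebo subjects is their first OLE dose.

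SAP 8.5 needs no replacement.

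The cost is SAP wording, one derived denominator and a few extra descriptive tables, with no new data collection. Two limits should be stated with the tables. Cycles of 21 and 28 days are mixed. Later cycles contain a selected group, because eligibility is rechecked each time and subjects leave when their regimen ends, so a flat or falling by-cycle pattern does not by itself show that risk is stable.

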## **9 SAFETY ASSESSMENTS**

### **9.1 Adverse Events**

An adverse event is defined as any untoward medical occurrence in a subject administered a pharmaceutical product, which does not necessarily have a causal relationship with this treatment. An adverse event can therefore be any unfavorable and/or unintended sign (including an abnormal laboratory finding), symptom, or disease temporally associated with the use of an investigational medicinal product, whether or not related to the investigational medicinal product. All adverse events, including observed or volunteered problems, complaints, or symptoms, are to be recorded on the appropriate eCRF.

Adverse events, which include clinical laboratory test variables, will be monitored and documented from the time of informed consent until the Follow-Up Visit occurring prior to (within 3 days) Chemotherapy Day in Cycle X + 3 (for subjects not continuing into the optional OLE Period) and the Follow-Up Visit occurring 30 days after last dose of IP (for subjects continuing into the optional OLE Period). Subjects should be instructed to report any adverse event that they experience to the Investigator. Beginning with the Screening Visit, Investigators should make an assessment for adverse events at each visit and record the event on the appropriate adverse event eCRF. Events associated with disease progression should not be reported as adverse events/SAEs. However, if in the Investigator's opinion the disease progression is manifesting in an unusual or uncharacteristic manner, the associated events should be reported as adverse events/SAEs, as appropriate.

Wherever possible, a specific disease or syndrome (ie, diagnosis) rather than individual associated signs and symptoms should be identified by the Investigator and recorded on the eCRF. However, if an observed or reported sign or symptom is not considered a component of a specific disease or syndrome by the Investigator, it should be recorded as a separate adverse event on the eCRF. Additionally, the condition that led to a medical or surgical procedure (eg, surgery, endoscopy, tooth extraction, or transfusion) should be recorded as an adverse event, not the procedure.

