Any medical condition already present at the Screening Visit should not be reported as an adverse event unless the medical condition or signs or symptoms present at baseline changes in severity, frequency, or seriousness at any time during the study. In this case, it should be reported as an adverse event.

Clinically significant abnormal laboratory or other examination findings that are detected during the study or are present at the Screening Visit and significantly worsen during the study should be reported as adverse events. The Investigator will exercise his or her medical and scientific judgment in deciding whether an abnormal laboratory finding or other abnormal assessment is clinically significant. Clinically significant abnormal laboratory values occurring during the clinical study will be followed until repeat tests return to normal, stabilize, or are no longer clinically significant. Laboratory abnormalities are not considered adverse events unless they are associated with clinical signs or symptoms, or require medical intervention. Any abnormal test that is determined to be an error does not require reporting as an adverse event.

Clinically significant abnormal findings in physical examinations will be reported as adverse events.

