#### Causality Assessment:

The relationship of an adverse event to the administration of the IP is to be assessed according to the following definitions:

- No (unrelated, not related, no relation) – The time course between the administration of IP and the occurrence or worsening of the adverse event rules out a causal relationship and another cause (concomitant drugs, therapies, complications, etc.) is suspected.
- Yes (related) – The time course between the administration of IP and the occurrence or worsening of the adverse event is consistent with a causal relationship and no other cause (concomitant drugs, therapies, complications, etc.) can be identified.

The definition implies a reasonable possibility of a causal relationship between the event and the IP. This means that there are facts (evidence) or arguments to suggest a causal relationship.

The following factors should also be considered:

- The temporal sequence from IP administration-
  - The event should occur after the IP is given. The length of time from IP exposure to event should be evaluated in the clinical context of the event.
- Underlying, concomitant, intercurrent diseases-
  - Each report should be evaluated in the context of the natural history and course of the disease being treated and any other disease the subject may have.
- Concomitant drug-
  - The other drugs the subject is taking or the treatment the subject receives should be examined to determine whether any of them might be recognized to cause the event in question.

- Known response pattern for this class of IP-
  - Clinical and/or preclinical data may indicate whether a particular response is likely to be a class effect.
- Exposure to physical and/or mental stresses-
  - The exposure to stress might induce adverse changes in the recipient and provide a logical and better explanation for the event.
- The pharmacology and PK of the IP-
  - The known pharmacologic properties (absorption, distribution, metabolism, and excretion) of the IP should be considered.

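### The TEAE definition has no worsening clause, so an adverse event that starts before the first dose and worsens on study drug can be missing from the adverse event tables

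*SAP*

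**What the plan says.** The SAP's rule is in section 9.2: "TEAEs are defined as AEs occurring after the first dose of study treatment". The same section confines the tabular adverse event summaries to these events. That covers the overview and the tables of related, Grade 3+, serious and special-interest events and of events leading to discontinuation. The listings are wider: they hold everything reported since consent, with a flag for treatment emergence. The protocol offers no other TEAE definition.

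Recording starts before counting. Under protocol 9.1, adverse events "will be monitored and documented from the time of informed consent until the Follow-Up Visit". The same section deals with pre-existing conditions. A condition present at Screening is not reportable "unless the medical condition or signs or symptoms present at baseline changes in severity, frequency, or seriousness at any time during the study", and it then says: "In this case, it should be reported as an adverse event".

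The protocol's causality assessment (9.1.1) treats worsening like a new event. An event is related when, among other conditions, "The time course between the administration of IP and the occurrence or worsening of the adverse event is consistent with a causal relationship".

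**The concern.** Subjects enter during a chemotherapy cycle in which they have been severely thrombocytopenic, so some may have an adverse event under way when they take their first dose. If such an event rises in grade or becomes serious on study drug, the change is what a safety comparison needs to show. Under a definition that looks only at whether the event came after the first dose, the change may not be counted. The tables that readers rely on most (serious, Grade 3+, related, special interest) would then understate post-dose worsening. The investigator could judge an event related because it worsened on study drug, yet the event would not appear among the related TEAEs.

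**Working it through.** No arithmetic decides this point. It comes from reading the collection rule, the recording rule and the counting rule together.

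**1. Length of the gap.** Protocol 6.2.1 places Screening from Day -28 to Day -1 and allows it to be combined with Baseline on the day before dosing. The interval between the start of collection and the first dose is therefore 1 to about 28 days.

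**2. What happens to each kind of event.**

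| Event | Recording (protocol 9.1) | Counting (SAP 9.2) |
|---|---|---|
| Starts after the first dose | Adverse event | TEAE |
| Present at Screening, worsens on study drug | Becomes reportable because it changed | TEAE if dated at the worsening, not if dated at original onset; neither document says which |
| Starts after Screening and before the first dose, then worsens | Already an adverse event; the Screening rule does not clearly reach it, and no new record is called for | Not a TEAE if the original onset date is kept |
| Starts on the day of the first dose | Adverse event | Unclear; the SAP names only a date of onset for its listings, and Baseline can be the first dosing day (protocol 6.2.2) |

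**3. Which outputs depend on the flag.** Only the adverse event tables in SAP 9.2. The following do not:
- the shift tables from baseline to worst post-baseline grade and the liver-test table (SAP 9.3);
- the ISTH bleeding table (SAP 9.4.2);
- the transfusion table (SAP 9.4.3);
- the listings.

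**4. Special-interest events.** There are two categories. Bleeding has its own ISTH table outside the filter. Thromboembolic events have nothing comparable in SAP 9.3 to 9.4, so their tabulation rests on the TEAE flag alone.

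**5. Open-label extension.** SAP 9.2 tabulates the extension separately but gives no rule for an event that starts earlier and worsens there. Study treatment includes placebo (SAP 4.3.3). For a subject randomized to placebo, an event that began in the Observational Period is already treatment-emergent, but nothing moves its worsening on first avatrombopag exposure into the extension tables.

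**6. Scale of one subject.** With the planned 80 and 40 subjects, and assuming all are dosed, one omitted subject changes a percentage by 1/80 = 1.25 points on avatrombopag and 1/40 = 2.5 points on placebo. This does not estimate how many are affected.

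**The case against.** The strongest reply is that protocol 9.1 already handles worsening. A Screening condition that changes becomes an adverse event because it changed and, if dated at the change, meets the SAP definition. The rule also mentions signs present at baseline, which arguably extends it to the Baseline Visit. This stands as a limit: the clear gap is the interval between Screening and the first dose, which may be a single day. It does not close the gap, because neither document sets the onset date of a worsened event.

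A second reply is that the SAP says occurring, not starting, so an ongoing event might count. On that reading every unchanged ongoing event becomes treatment-emergent. Neither reading isolates events that are new or worse.

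Several stronger conclusions are tempting and are not supported:

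- A reader might infer that worsened events vanish from all safety output. They do not: the outputs in step 3 carry no TEAE filter.
- A reader might infer that anything that began in the qualifying cycle is lost. The Screening rule works against that, and thrombocytopenia itself is generally not reported as an adverse event (protocol 9.1.3).
- A reader might take a minor bleed that becomes major as the leading example. Clinically significant bleeding must always be reported as a special-interest event (9.1.3), with a form due within 24 hours (9.1.2), and the ISTH table captures it by category. That table does not replace the serious, related or Grade 3+ tables, but the example is largely backed up.
- A reader might infer a bias in favor of avatrombopag. The rule is identical in both arms of a blinded, randomized comparison, and no direction is shown.

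For thromboembolic events, exclusion criterion 10 removes subjects with thrombosis in the 3 months around Screening, and eligibility is checked again at Baseline, so few cases should arise. The criterion is tied to Screening, however, and does not plainly cover an event that first appears afterwards.

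**Conclusion.** The point holds as a limited gap in definition. As written, SAP 9.2 can leave an adverse event that starts between Screening and the first dose, and then worsens on study drug, out of the Grade 3+, serious, related and special-interest tables. It can do the same to a condition present at Screening whose worsening is not entered as a new, newly dated event. The consequence is most relevant for thromboembolic events.

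This conclusion assumes that the flag is set from the recorded onset date and that sites do not open a new record at worsening; neither document settles either point. The documents give no rate of ongoing or worsening events, so the number of affected subjects cannot be derived. The expected harm is undercounting in both arms. The importance is minor, but the fix is cheap.

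**What to change.** In SAP 9.2, define a TEAE as an adverse event with onset on or after the first dose, or with earlier onset and an increase in CTCAE grade, frequency or seriousness on or after the first dose. Add three rules:

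- Worsening is dated on the day it occurs, and that date sets the flag.
- An event on the day of the first dose counts as treatment-emergent unless the record shows that it preceded dosing.
- The same logic assigns events to the open-label extension, so that worsening after the first extension dose appears in that period's tables.

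The cost is a few sentences in the SAP and a derived flag in the adverse event dataset, settled before unblinding. TEAE percentages will be slightly higher in both arms.
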